6.4.2. CS1001 Dose Suspension

CS1001 will be **suspended** for any of the following CS1001-related adverse reactions:

- Any Grade  $\geq 2$  non-skin, drug-related adverse event, with the following exceptions:
  - Grade 2 drug-related fatigue or laboratory abnormalities do not require a treatment delay
  - Grade 2 drug-related hypothyroidism/hyperthyroidism do not require a treatment delay
- Any Grade 3 skin, drug-related adverse event
- Any Grade 3 drug-related laboratory abnormality, with the following exceptions:
  - Grade 3 lymphopenia does not require dose delay
  - For a subject who has Grade  $\geq 2$  drug-related AST, ALT, or total bilirubin elevation, dose delay is required
  - Any Grade ≥3 drug-related amylase or lipase abnormalities not associated with symptoms or manifestations of pancreatitis do not require dose delay. If such Grade ≥ 3 amylase or lipase abnormalities occur, the sponsor's medical monitor should be consulted
- Any adverse event, laboratory abnormality, or intercurrent illness which, in the judgment of the investigator, warrants delaying the dose of CS1001.

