## 6.4.3. CS1001 Dose Resumption

Subjects may resume treatment with CS1001 when the CS1001-related AE(s) resolve to Grade  $\leq 1$  or baseline within 9 weeks from the scheduled dosing, with the following exceptions:

- Subjects may resume treatment in the presence of Grade 2 fatigue.
- Subjects who have not experienced a Grade 3 drug-related skin AE may resume

treatment if the event recovers to Grade  $\leq 2$  skin toxicity.

- Subjects with combined Grade 2 AST/ALT and total bilirubin values meeting discontinuation parameters should have treatment permanently discontinued.
- Drug-related pulmonary toxicity, diarrhea, or colitis must be completely resolved to baseline level before treatment is resumed. For patients with Grade 1 pneumonitis despite steroid tapering for at least 1 month, treatment may be resumed after discussion with and approval by the sponsor's medical monitor.
- Drug-related endocrinopathies adequately controlled with only physiologic hormone replacement may resume treatment after consultation with the sponsor medical monitor.

Two dose delays are allowed due to toxicity. If the need for third delayed administration of toxicity occurs, after consultation with the sponsor, the study treatment will be permanently terminated.

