# 14.3. APPENDIX 3: GUIDANCE FOR IMMUNE-RELATED ADVERSE REACTIONS MANAGEMEMT

Identification, diagnosis, management of immune-related adverse events and dose adjustment method are listed in detail as following:

irAE	Potential signs and symptoms	Diagnosis and differential diagnosis	Recommended management	Dose modification
Pneumonitis	Symptomatic : dyspnea, cough, pleuritic chest pain, hypoxia Asymptomati c: lung infiltrates that mimic severe bacterial pneumonia	
 
Radiographic imaging of chest
 
Observe the specimen of tissues and lavage fluids used in bronchoscopy to investigate infectious pathogens and perform a pathologic evaluations on them
 
	Moderate (Grade 2): administration of corticosteroids at a dose of 1-2 mg/kg/day prednisone equivalents Severe (≥ Grade 3): high dose corticosteroids (2-4 mg/kg/day IV methylprednisolone) along with antibiotics; in-patient hospitalization; consultation with a respiratory physician; additional immunosuppression with infliximab can be considered	Withhold the administration of CS10 until resolved to ≤ Grade 1 Permanent discontinuation from the study
Colitis	Watery diarrhea, mucus or blood in stool, abdominal pain, nausea/vomiti ng, dehydration, peritoneal signs, bowel perforation	
 
Stool cultures
 
Endoscopy or colonoscopy to rule out infection
 
Biopsy to rule out alternative etiology
 
	Moderate (≤Grade 2) diarrhea: antidiarrheal medication, oral hydration, electrolyte supplement Persistent Moderate (Grade 2) diarrhea: administration of corticosteroids at a dose of 1-2 mg/kg/day prednisone equivalents Severe (Grade 3) diarrhea: high dose corticosteroids (2-4 mg/kg/day IV methylprednisolone) along with antibiotics; infliximab can be	Continue dosing Withhold the administration of CS1001 until resolved to $\leq$ Grade 1 Withhold the administration of CS1001 until resolved to $\leq$ Grade 1

Recurrent severe (Grade 3) or life- threatening (Grade 4): high dose corticosteroids (2-4 mg/kg/day IV methylprednisolone)		considered for steroid refractory diarrhea
high dose corticosteroids (2-4 mg/kg/day IV	discontinuation	
corticosteroids (2-4 mg/kg/day IV	from the study	threatening (Grade 4):
mg/kg/day IV		high dose
		corticosteroids (2-4
methylprednisolone)		mg/kg/day IV
along with antibiotics;		methylprednisolone)

irAE	Potential signs	Diagnosis and	Recommended	Dose modification
	and symptoms	differential	management	
		diagnosis	8	
			infliximab can be	

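### For CS1001-related diarrhoea or colitis managed as an irAE, Section 6.4 and Appendix 3 give different hold and restart rules for CS1001

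*Protocol*

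**What the plan says.** **Hold.** Protocol 6.4.2 suspends CS1001 for any CS1001-related event of Grade 2 or higher in the class "non-skin, drug-related adverse event, with the following exceptions". The Grade 2 exceptions are "Grade 2 drug-related fatigue or laboratory abnormalities do not require a treatment delay" and "Grade 2 drug-related hypothyroidism/hyperthyroidism do not require a treatment delay". Skin events have their own threshold: "Any Grade 3 skin, drug-related adverse event". Diarrhoea and colitis are not excepted.

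The colitis row of Appendix 3 (14.3) treats diarrhoea of Grade 2 or less with "antidiarrheal medication, oral hydration, electrolyte supplement". Its next tier is "Persistent Moderate (Grade 2) diarrhea: administration of corticosteroids at a dose of 1-2 mg/kg/day prednisone equivalents", followed by Grade 3. The dose column, whose adjacent entries run together in the text available to me, begins "Continue dosing Withhold the administration of CS1001 until resolved to" Grade 1 or less, and then gives a second withhold entry.

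**Restart.** The general rule in 6.4.3 is Grade 1 or less, or baseline, within 9 weeks. It then makes a named exception: "Drug-related pulmonary toxicity, diarrhea, or colitis must be completely resolved to baseline level before treatment is resumed". For pneumonitis it allows residual Grade 1 only after at least 1 month of steroid taper and with medical-monitor approval. Section 6.6.3 lets CS1001 restart once an irAE is held at Grade 1 or better, and Appendix 3 withholds until Grade 1 or less.

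**Links between the texts.** Section 6.6.3 refers the reader to Appendix 3 for irAE dose adjustment. A footnote to 6.4.1, the BLU-554 section, advises considering Appendix 3 when an immune cause cannot be excluded.

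**The concern.** Suppose a subject has Grade 2 diarrhoea that is attributed to CS1001, managed as immune-related and not persistent when the next infusion is due. Section 6.4.2 says suspend and Appendix 3 says continue. The subject later improves to Grade 1 from a Grade 0 baseline. Section 6.4.3 forbids restart, while Appendix 3 and 6.6.3 permit it. The second step is re-exposure to a PD-L1 antibody before an event that 6.4.3 singles out has cleared.

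Sites could handle the same event differently. Dose delays, dose intensity and dose adjustment are summarised under SAP 3.5.1, and discontinuation is part of the Phase II secondary tolerability endpoint, so inconsistent handling could reach those summaries.

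**Working it through.** No design figure is involved. The check compares the rules.

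**1. Hold rule for colitis.** The row's first cell has three diarrhoea tiers (Grade 2 or less; persistent Grade 2; Grade 3) and three dose entries in the same order (continue; withhold; withhold). Separate tiers for Grade 2 or less and persistent Grade 2 make sense only if the first continues dosing. The row gives no duration for persistent. Non-persistent Grade 2 is therefore suspended under 6.4.2 and continued under Appendix 3. Section 6.6.3 sets no grade for suspension, so it does not conflict here.

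**2. Is Appendix 3 looser throughout?** It has four entries that continue dosing:
- hypothyroidism, Grade 2 or less: matches the thyroid exception in 6.4.2
- hyperthyroidism, Grade 2 or less: matches the same exception
- dermatitis, Grade 2 or less: matches the Grade 3 skin threshold
- colitis, Grade 2 or less: no match

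So 4 − 3 = 1 entry is unmatched. That looks more like a drafting mismatch than a policy.

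**3. Restart rules.**

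| Event | 6.4.3 | Appendix 3 | Stricter text |
|---|---|---|---|
| Diarrhoea/colitis | Baseline | Grade ≤1 | 6.4.3 |
| Pneumonitis | Baseline; residual Grade 1 only after ≥1 month of taper, with approval | Grade ≤1 | 6.4.3 |
| Hypophysitis, Grade 2 without adrenal crisis | Also allowed when controlled on physiologic hormone replacement, after consultation | Grade ≤1 | Appendix 3 |
| Grade 3 thyroid | Grade ≤1 or baseline, or controlled on replacement after consultation | Asymptomatic Grade 2, Grade ≤1 or baseline; no consultation | Mixed |
| Grade 3 dermatitis | Grade ≤1 or baseline (the Grade 2 allowance excludes subjects who have had a Grade 3 skin event) | Grade ≤2 | 6.4.3 |

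For colitis the texts part only at residual Grade 1 with baseline below Grade 1. With a Grade 1 baseline there is no conflict.

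**4. Precedence.** The 6.6.3 reference and the advisory 6.4.1 footnote are cross-references, not rankings. Sections 6.4.2 and 6.4.3 do not exclude irAEs, and 6.4.3 names colitis.

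**5. What falls outside.** Diarrhoea attributed to BLU-554 alone comes under 6.4.1. CS1001-related diarrhoea judged non-immune comes under 6.4.2 and 6.4.3. If the responsible drug cannot be judged, 6.4 suspends both.

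**6. Reach.** CS1001 is given once per 21 days, and Day 1 has a ±4-day window from Cycle 2 (Schedule of Activities). The hold conflict needs the event to be present when a dose is due. A toxicity delay is used only if recovery outlasts the window.

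**The case against.** The best case against the point has four parts.

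- **Restart resolves itself.** Section 6.4.3 is specific and mandatory for diarrhoea and colitis, while 6.6.3 and Appendix 3 are permissive and restate the general rule. On an ordinary specific-over-general reading, baseline governs. This largely stands. The restart half is a case of one text permitting what another forbids, and a compliant course exists.
- **The hold has an implied answer.** Section 6.4 says a subject with CS1001-related toxicity must suspend or stop, and Appendix 3 is titled as guidance. However, 6.6.3 sends irAE dose adjustment to that guidance, which implies the opposite. Two plausible readings with opposite results are the problem, so this does not remove it.
- **Clinical judgement is allowed.** Section 6.4 permits decisions on clinical circumstance, with departures documented and communicated to the sponsor. That makes differences more visible but does not say which rule is being departed from.
- **Consequences are small.** The Day 1 window means a delay is not automatic, 6.6.3 has the sponsor told of Grade 2 irAEs that need suspension, and the sponsor is consulted before treatment ends at a third delay. This stands and limits the severity.

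A reader might take the 76% rate of related diarrhoea on BLU-554 alone (87 of 115) as the size of the problem. It is not: it covers a different drug, all grades and any timing. Diarrhoea is listed among the irAEs on CS1001 alone (4.2.2), without its own count or grade.

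**Conclusion.** The contradiction holds for CS1001-related diarrhoea or colitis managed as an irAE. The hold rules are incompatible at non-persistent Grade 2 on a dosing day. The restart rules differ only at residual Grade 1 above baseline, where waiting for baseline satisfies every text. Restart mismatches are not limited to colitis and pneumonitis: the hypophysitis, Grade 3 thyroid and Grade 3 dermatitis rows differ too, not all in the same direction.

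The size is minor and concerns safety conduct. The documents give no rate for either triggering situation, so the number of subjects affected cannot be computed.

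A reader might infer that the dose-finding result or the response rate is compromised. The documents do not support that. Phase Ib recruitment was completed on 20 May 2020 and the RP2D was confirmed on 18 June 2020, and nothing links these rules to a change in DLT counts or ORR.

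The conclusion assumes that the tiers and dose entries in the colitis row correspond in order, as the row's structure indicates.

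**What to change.** 1. In the Appendix 3 colitis row, withhold CS1001 at any Grade 2 CS1001-related diarrhoea and restart only at baseline.
2. In the pneumonitis row, carry over the 6.4.3 conditions: baseline, or residual Grade 1 after at least 1 month of taper with medical-monitor approval.
3. Make the 6.6.3 restart sentence subject to the exceptions in 6.4.3.
4. State that where 6.4 and Appendix 3 differ, the more restrictive hold or restart rule applies. Alternatively, reconcile the hypophysitis, thyroid and dermatitis rows in the same amendment.

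A blanket statement that 6.4.2 and 6.4.3 govern is not advised. It would leave those three rows contradicting the governing text and would relax the hypophysitis restart.

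The cost is amendment wording and a memo to sites, with no extra procedures or patients. The downside is a few more CS1001 delays, each counting toward the two permitted for toxicity.

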## 6.4.4. CS1001 Permanent Discontinuation

Subjects will be required to permanently discontinued CS1001 for the following drug relatedadverse events:

- Any Grade 2 CS1001-related uveitis, eye pain or blurred vision that does not respond to topical therapy and does not improve to Grade 1 severity within the re-treatment period OR requires systemic treatment.
- ≥ Grade 3 infusion-related reaction during or after CS1001 infusion see Section 错误!未找到引用源。
- Grade 3-4 severe pneumonitis
- Any Grade 3 non-skin, drug-related adverse event lasting > 7 days, with the following exceptions:
  - Grade 3 drug-related uveitis, pneumonitis, bronchospasm, hypersensitivity reaction, or infusion reaction of any duration requires discontinuation.
  - Grade 3 drug-related endocrinopathies adequately controlled with only physiologic hormone replacement do not require discontinuation.
  - Grade 3 drug-related laboratory abnormalities do not require treatment discontinuation except:
    - Grade 3 drug-related thrombocytopenia >7 days or serious uncontrollable bleeding event requires discontinuation;
    - any drug-related liver function test (LFT) abnormalities that meet the following criteria requires discontinuation:
      - AST or ALT > 5-10  $\times$  ULN for 2 weeks
      - AST or ALT  $> 10 \times ULN$
      - Total bilirubin  $> 5 \times ULN$
      - Concurrent AST or ALT >  $3 \times$  ULN and total bilirubin >  $2 \times$  ULN
- Any Grade 4 drug-related adverse event or laboratory abnormality, except for the following events which do not require discontinuation:
  - Grad4 neutropenia  $\leq$  7 days

- Grade 4 lymphopenia or leukopenia
- Isolated Grade 4 electrolyte imbalances/abnormalities that are not associated with clinical sequelae and are corrected with supplementation/appropriate management within 72 hours of their onset.
- Grade 4 drug-related endocrinopathy adverse events, such as adrenal insufficiency, ACTH deficiency, hyper- or hypothyroidism, or glucose intolerance, which resolve or are adequately controlled with physiologic hormone replacement (corticosteroids, thyroid hormones) or glucose-controlling agents, respectively, may not require discontinuation after discussion with and approval from the sponsor Medical Monitor.
- Any event that leads to delay in dosing lasting > 9 weeks from the scheduled dosing requires discontinuation, with the following exceptions:
  - Dose delays to allow for prolonged steroid tapers to manage drug-related adverse events may be allowed if approved by the sponsor medical monitor. Prior to re-initiating treatment in a subject with a dosing delay lasting > 9 weeks from the scheduled dosing, the sponsor medical monitor must be consulted. Tumor assessments should continue as per protocol even if dosing is delayed. Periodic study visits to assess safety and laboratory studies should also continue, more frequently study visit should take if clinically indicated during such dosing delays.
  - Dosing delays lasting > 9 weeks from the scheduled dosing that occur for nondrug-related reasons may be allowed if approved by the sponsor medical monitor. Prior to re-initiating treatment in a subject with a dosing delay lasting > 9 weeks, the sponsor medical monitor must be consulted. Tumor assessments should continue as per protocol even if dosing is delayed. Periodic study visits to assess safety and laboratory studies should also continue, more frequently study visit should take if clinically indicated during such dosing delays.

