# 5.6. TREATMENT DISCONTINUATION AND STUDY WITHDRAWAL

### 5.6.1. Criteria for Study Treatment Discontinuation

Subjects will discontinue the study drug treatment if any of the following occurs:

- 1. Study protocol-specified discontinuation criteria (see Section 错误!未找到引用源。 and6.4.4).
- 2. Any clinical adverse events (AEs) or concurrent diseases that, in the opinion of the investigator, indicate continued participation is not in the best benefit of the subject
- 3. Disease progression (subjects who meet the criteria for re-challenge after disease progression may continue medication until the progression is confirmed by imaging evaluation)
- 4. Any progression or recurrence of any malignancy, or any occurrence of another malignancy that requires active treatment
- 5. Poor compliance from subjects, untimely and quantitative medication, failure of communication by investigators, or may lead to large deviation of test results and can't be remedied, these will result in the discontinuation of study drug after confirmation of investigators and the sponsor.
- 6. During the study treatment, for any subject who receives any prohibited comedications and/or concomitant treatments that affect the tolerance judgment, the investigators and the sponsor can make subjects withdraw from the study drug treatment after confirmation.
- 7. Subjects, who are reluctant to continue the clinical trial, can inform to doctor in charge at any time, and can withdraw from it immediately. In accordance with the Helsinki Declaration and other applicable statutes and regulations, subjects are entitled to withdraw from the study at any time for any reason, and the doctor or site can't hold prejudice against his future medical care.

- 8. Other cases that the investigators consider unsuitable for continued medication.
- 9. Female subject becomes pregnant
- 10. Death
- 11. Follow-up

If a subject fails to complete the study for non-drug related reasons, it will be considered that the subject did not finish the study; if the sponsor considers it is necessary, and then the number of subjects should be supplemented. The decision of subjects should be recorded.

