**Infusion Reactions of CTCAE Level 3 or 4:** The infusion should be discontinued immediately. Appropriate medical management strategies should be established immediately according to severity and type of the reaction. It includes but is not limited to oral or intravenous antihistamines, antipyretic agents, corticosteroids, epinephrine, bronchodilators and oxygen.

Whenever the subject occurs an infusion-related reaction of Level 4, CS1001 must be discontinued.

If an infusion-related reaction of Level 3 occurs, whether to continue the study treatment will be determined by the investigator after consulting with the sponsor. If it is decided to continue the treatment, the infusion time of CS1001 should be at least 1 hour for **the next dosing period**. Prophylactic antihistamines (e.g., diphenhydramine 50 mg or equivalent drugs) and antipyretic agents (e.g., paracetamol, non-steroidal anti-inflammatory drugs (NSAIDs) or equivalent drugs) will be given within 30 to 60 minutes prior to infusion. The subject will be closely monitored for infusion-related clinical signs and symptoms.

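### After a Grade 3 CS1001 infusion reaction, Protocol 6.4.4 requires permanent discontinuation but 6.6.1 allows re-dosing, and nothing says which governs

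*Protocol*

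**What the plan says.** Protocol 6.4.4 lists events after which CS1001 must be stopped for good. Infusion reactions appear twice. One bullet, with a threshold of Grade 3 or higher, names a "Grade 3 infusion-related reaction during or after CS1001 infusion". A later sub-bullet, on Grade 3 events, says: "Grade 3 drug-related uveitis, pneumonitis, bronchospasm, hypersensitivity reaction, or infusion reaction of any duration requires discontinuation".

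Protocol 5.6.1 opens with "Subjects will discontinue the study drug treatment if any of the following occurs", and its first item is "Study protocol-specified discontinuation criteria", citing 6.4.4 together with another section whose reference cannot be read.

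Protocol 6.6.1 manages infusion reactions by level, under a paragraph headed "Infusion Reactions of CTCAE Level 3 or 4". It reserves the mandatory stop for the higher level: "Whenever the subject occurs an infusion-related reaction of Level 4, CS1001 must be discontinued". For Level 3, "whether to continue the study treatment will be determined by the investigator after consulting with the sponsor". It continues: "If it is decided to continue the treatment, the infusion time of CS1001 should be at least 1 hour". That infusion is at the next dosing period, with antihistamine and antipyretic premedication 30 to 60 minutes beforehand.

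Table 9 in 6.6.1 puts Level 3 and Level 4 in one row. Its treatment cell holds one sentence leaving continuation of study treatment to the investigator and another saying that no more CS1001 is to be given.

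**The concern.** The same clinical event triggers a permanent stop in one section and a described procedure for the next infusion in another. Level 3 is not a mild category. Table 9 describes it as delayed relief, relapse after initial improvement, or hospitalization or other clinical consequences. Staff dealing with such a reaction will naturally turn to 6.6.1, and there they will find instructions for giving CS1001 again. Nothing in that paragraph tells them that 6.4.4 forbids it.

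The main stake is subject safety. A smaller one is consistency: up to 20 sites are planned, and sites could handle identical reactions differently. Discontinuation of study drug is a Phase II secondary tolerance endpoint, and the SAP tabulates both infusion-related reactions and events leading to discontinuation.

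**Working it through.** The conflict is textual, so the check sets the rules side by side for one case: a Grade 3 infusion-related reaction to CS1001.

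| Place in Protocol | What it says about further CS1001 |
|---|---|
| 6.4.4, first bullet | Permanent stop at Grade 3 or higher; carries a cross-reference that cannot be read |
| 6.4.4, later sub-bullet | Permanent stop at Grade 3, whatever the duration; no cross-reference |
| 6.6.1, Level 3 paragraph | May be given at the next dosing period after sponsor consultation |
| 6.6.1, Level 4 sentence | Mandatory stop, stated for Level 4 only |
| 6.6.1, Table 9, Level 3/4 row | Both investigator discretion and no further CS1001 |
| 6.4, general guidance | Follow the guidelines, weigh clinical circumstance, document and communicate departures; no order of precedence |

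1. *Is it the same event on the same scale?* Yes. The 6.6.1 paragraph and Table 9 use CTCAE levels, and 6.4 grades events by CTCAE version 5.0.
2. *Could continuing treatment in 6.6.1 mean BLU-554 alone?* Not in the Level 3 paragraph. The sentence that follows sets the infusion time for CS1001, and the preceding sentence reserves the mandatory CS1001 stop for Level 4.
3. *Is 6.6.1 an exception that 6.4.4 allows for?* 6.4.4 does not say so. Where it wants sponsor-approved exceptions it writes them in, as for Grade 4 endocrine events and for dosing delays beyond 9 weeks. It gives none for infusion reactions. If the unreadable reference in the first bullet pointed to 6.6.1, the later sub-bullet would still stand alone.
4. *Does Table 9 decide?* No. Its Level 3/4 cell contains two blocks, each with its own closing line on medical management. They may be separate Level 3 and Level 4 instructions that ran together when the PDF was read. If so, the Level 3 block sides with the 6.6.1 paragraph and still contradicts 6.4.4. If not, the cell contradicts itself or is unclear. The conflict between 6.4.4 and 6.6.1 survives either way.
5. *Is there a neighbouring text with the same problem?* Yes. 6.6.2 says that a subject with a generalized allergic reaction should stop study drug. It then advises prophylaxis before each later CS1001 infusion if such reactions follow the first treatment. The 6.4.4 sub-bullet covers hypersensitivity and bronchospasm as well, so correcting 6.6.1 alone would leave this re-dosing wording in place.

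*Size.* Protocol 2.4.1.2 reports 0 infusion-related treatment-emergent events in 29 CS1001 monotherapy subjects. The one-sided 95% upper limit for the any-grade proportion is 1 − 0.05^(1/29) = 0.098, or 9.8%. For the approximately 40 planned Phase II subjects that is at most 40 × 0.098 = 3.9, about four subjects with a reaction of any grade. Grade 3 events would be a subset. This assumes that the monotherapy rate carries over to the combination, and the documents give no Grade 3 rate. The issue applies mainly to Phase II because Phase Ib recruitment closed on May 20, 2020.

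**The case against.** The best defence is that the protocol already contains the risk. Re-dosing under 6.6.1 needs consultation with the sponsor, 6.4 requires departures to be documented and communicated, and stopping CS1001 is compliant everywhere. The Level 3 paragraph also looks deliberate, since it specifies premedication, its timing and an infusion time. The documents do not show which rule the sponsor intended. All of this stands, and it limits the weight of the point. It does not settle the rule: a sponsor representative who is consulted has the same two opposing texts to work from.

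Three stronger readings are tempting and should not be relied on:

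- A reader might count sentences and conclude that stopping outnumbers continuing. The count depends on how the merged-looking Table 9 cell is read, so it shows nothing.
- A reader might take 5.6.1 as proof that 6.4.4 prevails. Its first item also cites a section that cannot be read. If that section is 6.6 or 6.6.1, then 5.6.1 favours neither rule.
- A reader might reconcile Table 9 with 6.4.4 by supposing that the investigator's discretion there covers BLU-554 only. No section says so. The provision in 6.4 for one product to continue concerns suspension of the other, not permanent discontinuation.

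**Conclusion.** The contradiction is real and confined to one branch: giving CS1001 again after a Grade 3 infusion reaction. 6.4.4 forbids it, the Level 3 paragraph of 6.6.1 permits it, and neither the rest of the protocol nor the SAP ranks them. This conclusion rests on 6.4.4 and that paragraph alone and does not depend on the layout of Table 9.

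It should be corrected because a site can follow the protocol's own infusion-reaction section and still re-expose a subject whom another section bars. Few subjects are likely to be affected, but 29 monotherapy subjects cannot exclude an occasional event.

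A reader might infer that the efficacy conclusions are at risk. The documents do not support that. The ORR definition and the go/no-go thresholds do not refer to CS1001 discontinuation, treated subjects stay in the analysis, and tumour assessments continue after a stop for toxicity.

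**What to change.** Make the stricter rule in 6.4.4 govern, and align the other places with it:

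- In 6.6.1, delete the Level 3 continuation paragraph and extend the mandatory CS1001 stop to both Level 3 and Level 4.
- In Table 9, state that no further CS1001 is given after a Level 3 or Level 4 reaction, and that any decision to continue study treatment does not include CS1001.
- In 6.6.2, limit the prophylaxis advice so that it cannot be read as allowing CS1001 after a hypersensitivity reaction that is generalized or of Grade 3 or higher.
- Send the sites a clarification letter.

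If the sponsor does want rechallenge after Grade 3, the exception and its conditions should be written into 6.4.4 and repeated in 6.6.1 and Table 9. The stricter rule is the safer default because it is already stated without exception.

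The cost is protocol wording and a letter, with no change to design, sample size or analysis. The downside is that a few subjects lose the option of CS1001 rechallenge.

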6.6.3. Immune-Related Adverse Events

If an immune-mediated AE is suspected, the investigator should ensure that the evidence of etiology is conclusive or other causes may be excluded.

For any irAE of  $\geq$  Grade 3 or irAE of Grade 2 with the requirement of drug suspension or permanent withdrawal, the investigator should inform the sponsor as soon as possible and consult with the sponsor if necessary.

Based on the severity of AE, CS1001 will be suspended and corresponding treatment will be given. For subjects who use corticosteroids, corticosteroid dose will be gradually reduced within at least 1 month after the adverse reaction is improved to grade 1 or better. Short-term immunosuppressive agents such as tumor necrosis factor antagonists, mycophenolate mofetil or other drugs may be used if needed. If the severity of AE is maintained at grade 1 or better, CS1001 treatment can be restarted. In the event of an immune-mediated persistent, worsening or recurrent adverse event of Grade 3, or an immune- mediated event of Grade 4, CS1001 treatment should be discontinued permanently. For the identification, diagnosis, management and dose adjustment of irAE, please refer to APPENDIX 3: GUIDANCE FOR IMMUNE-RELATED ADVERSE REACTIONS MANAGEMEMT

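### Sections 6.4.3/6.4.4, 6.6.3 and Appendix 3 give different CS1001 actions for the same severe immune-related events, and no readable text says which governs

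*Protocol*

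**What the plan says.** The Protocol sets rules for stopping or resuming CS1001 in four places.

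- **6.4.3 (resumption).** In general, CS1001 may resume once a related event is back to Grade 1 or lower, or to baseline, within 9 weeks of the scheduled dose. Two exceptions matter here: "Drug-related pulmonary toxicity, diarrhea, or colitis must be completely resolved to baseline level before treatment is resumed", and "Drug-related endocrinopathies adequately controlled with only physiologic hormone replacement may resume treatment after consultation with the sponsor medical monitor".
- **6.4.4 (permanent discontinuation).** This is a list of required stops. It includes "Any Grade 3 non-skin, drug-related adverse event lasting > 7 days, with the following exceptions". One of those exceptions is "Grade 3 drug-related endocrinopathies adequately controlled with only physiologic hormone replacement do not require discontinuation". Related Grade 4 events also stop, but an endocrine event that resolves or is adequately controlled "may not require discontinuation after discussion with and approval from the sponsor Medical Monitor".
- **6.6.3 (immune-related events).** CS1001 can restart at Grade 1 or better. It is stopped permanently for an "immune-mediated persistent, worsening or recurrent adverse event of Grade 3". The Grade 4 sentence carries no endocrine exception: "mediated event of Grade 4, CS1001 treatment should be discontinued permanently". The section then refers irAE dose adjustment to Appendix 3.
- **Appendix 3 (14.3).** This is a table of actions by event and grade. It stops CS1001 permanently at Grade 3 or higher for hypophysitis, nephritis, neuromuscular toxicity and the group of other irAEs, which includes adrenal insufficiency. For Grade 3 diarrhea it withholds until Grade 1 or lower.

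**The concern.** An investigator facing a severe immune-related event can find two or three different instructions in the same protocol, depending on the section opened. The decision is whether to re-expose a patient to the drug that may have caused the event, so the first stake is patient safety. The second is the tolerance endpoint (discontinuation and dose reduction of study drug). Phase Ib recruitment was completed on 20 May 2020 (4.3.1), so this now matters mainly as a Phase II secondary endpoint. The SAP tabulates reasons for ending treatment (3.3.1) and adverse events leading to discontinuation (3.5.3). If sites apply different rules, those counts partly reflect which section was used.

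**Working it through.** No arithmetic applies. The check sets the texts side by side for the same event and grade, then looks for wording that ranks them. The rows are examples, not a complete list.

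| Event | 6.4.3 / 6.4.4 | 6.6.3 | Appendix 3 |
|---|---|---|---|
| (a) Grade 3 hypophysitis or adrenal insufficiency, controlled on replacement | Stop not required; resumption after Medical Monitor consultation | Stop only if persistent, worsening or recurrent | Permanent stop |
| (b) Grade 4 endocrinopathy, resolved or controlled | May continue with Medical Monitor approval | Permanent stop | Permanent stop for hyperthyroidism, hypophysitis and adrenal insufficiency; withhold only for hypothyroidism |
| (c) First Grade 3 nephritis, neuromuscular or other listed irAE, resolving within 7 days | 6.4.4 does not require a stop; 6.4.3 allows resumption at Grade 1 or lower, or baseline | Restart at Grade 1 or better | Permanent stop |
| (d) First Grade 3 diarrhea/colitis | 6.4.4 requires a stop if it lasts more than 7 days; 6.4.3 requires return to baseline before resuming | Permanent stop if persistent | Withhold to Grade 1 or lower, with no day limit |

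**Rows (a) to (c).** The 6.4.3/6.4.4 wording is permissive. A site that stops under Appendix 3 breaches nothing, and a site that continues under 6.4.3/6.4.4 also appears compliant. In row (b), Grade 4 hypothyroidism receives three different answers.

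**Row (d).** The problem is different. The 7-day stop and the return to baseline are mandatory, and the table that 6.6.3 points to contains neither. A site working from that table alone could re-dose a patient whom 6.4.4 requires to stop, or resume before the condition in 6.4.3 is met.

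**Search for precedence.** Four texts come close, and none ranks the sources.

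1. 6.6.3 refers irAE dose adjustment to Appendix 3 but has no override wording. It also differs from Appendix 3 in rows (a) to (d).
2. A footnote under 6.4.1, the BLU-554 rules, tells the investigator only to consider Section 14.3 when an immune cause cannot be excluded.
3. 5.6.1 refers discontinuation criteria to 6.4.4 and to another section whose number is unreadable in the available copy.
4. The opening of 6.4 lets individual decisions also rest on the clinical circumstance, with deviations documented and communicated to the sponsor.

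Because some cross-references did not resolve, the claim is limited to readable text.

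**The case against.** The strongest reply is that 6.4 covers drug-related events in general and Appendix 3 covers immune-related ones. Two texts point toward the appendix, so it could be read as the specific rule. This is a natural reading, but it does not settle the matter. Neither pointer says that Appendix 3 overrides anything. Section 6.4.4 itself names events that are commonly immune-related, such as pneumonitis, uveitis and endocrinopathies. In row (d) this reading would also displace two mandatory rules in favor of a looser table.

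A second reply is that a careful site would apply the strictest rule. That is sensible, but no readable text says so.

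A third reply is that oversight limits the consequences, and this largely stands. Under 6.6.3 the sponsor is told of every irAE of Grade 3 or higher as soon as possible. Continuing after a Grade 4 endocrine event needs Medical Monitor approval, and endocrine resumption needs consultation. Appendix 3 is titled as guidance. These provisions reduce the risk, but the person consulted has no written precedence rule either.

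A reader might also be tempted by stronger readings, which the documents do not support:

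- **All irAEs conflict.** They do not. Grade 3-4 pneumonitis is a permanent stop in both 6.4.4 and Appendix 3, and asymptomatic Grade 2 thyroid events continue under both 6.4.2 and Appendix 3.
- **Both sites would be compliant in every row.** This fails for (d), where resuming contrary to 6.4.3 or 6.4.4 breaches mandatory text.
- **The bilirubin limits also conflict.** The Appendix 3 hepatitis entry shows a limit of 3 x ULN against 5 x ULN in 6.4.4. The table is broken there, so its scope cannot be read. With AST or ALT above 3 x ULN, 6.4.4 already stops at bilirubin above 2 x ULN, so Appendix 3 is not uniformly stricter. This is left out.
- **Appendix 3 removes patients from the study.** Its wording says so, but 5.6.2 requires follow-up after drug discontinuation. This is a wording error only.

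**Conclusion.** The inconsistency is real in the readable text. In (a) to (c), two sites can treat the same event differently and both appear to follow the protocol. In (d), the referenced table omits rules that other sections make mandatory. Severity is minor to moderate: the action concerns patient safety, but existing oversight softens it, and the endpoint affected is a descriptive secondary summary in a single-arm phase of about 40 subjects.

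The events are expected to be uncommon. A reader might want a rate. The documents give none for the combination or for the disputed events, so no figure is offered. A reader might also infer an effect on ORR, DOR, PFS or OS. The documents give no basis for sizing one, and none is claimed.

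The conclusion assumes that the unresolved cross-references do not lead to a precedence statement.

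**What to change.** Amend the protocol as follows.

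1. Add the 7-day stop and the return-to-baseline condition to the diarrhea/colitis row of Appendix 3.
2. Write one endocrine rule, covering Grade 3 and Grade 4, in identical words in 6.4.4, 6.6.3 and Appendix 3. The sponsor may keep an exception for events controlled on replacement, provided that it needs Medical Monitor approval in all three places.
3. Align the Grade 3 rule for nephritis, neuromuscular toxicity and the other listed irAEs across 6.4.3/6.4.4, 6.6.3 and Appendix 3.
4. State that the stricter text applies wherever differences remain. A bare sentence giving Appendix 3 priority would be wrong, because without item 1 it would remove the mandatory colitis rules.
5. In the dose-modification column of Appendix 3, replace the wording that ends participation in the study with permanent discontinuation of CS1001, follow-up continuing per 5.6.2.

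The cost is amendment wording and a site memo, with no new procedures or subjects. The downside is that a few subjects may stop CS1001 who could have resumed under the present 6.4.3/6.4.4; any retained endocrine exception limits this.
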